4.4.2 Secondary Efficacy Endpoints

4.4.2.1 Progression-Free Survival

PFS, as determined by the IRC according to RECIST v1.1, will be analyzed using the same methods described for PFS analysis in Section [4.4.1](#).

4.4.2.2 Objective Response Rate

Objective response rate (ORR) is defined as the proportion of patients who had an objective response as assessed by the investigator. Objective response is defined as a CR or PR on two consecutive occasions at least 4 weeks apart, as determined by the investigator using RECIST v1.1. Patients evaluable for objective response will be all randomized patients with measurable disease at baseline. Randomized patients with measurable disease at baseline, who had no post-baseline tumor assessments, are considered non-responders.

A 95% Clopper-Pearson CI will be calculated for the ORR for each treatment arm. The difference in ORR between treatment arms will be tested using the stratified Cochrane-Mantel-Haenszel test. A 95% Hauck-Anderson CI will be calculated for the difference in ORR between treatment arms.

4.4.2.3 Duration of Response

For patients who achieve an objective response, DOR is defined as the time from the first occurrence of a documented objective response to disease progression, as determined by the investigator according to RECIST v1.1, or death from any cause, whichever occurs first. The censoring method for DOR will be the same as that for PFS. The Kaplan-Meier approach will be used to estimate median DOR. The 95% CI of the median DOR will be constructed using the Brookmeyer and Crowley method ([Brookmeyer and Crowley 1982](#)).

4.4.2.4 Overall Survival

OS is defined as the time from randomization to death from any cause. For patients who are alive at the time of analysis data cut-off, OS time will be censored at the date the patient was last known to be alive. Survival time for patients without post-baseline survival information will be censored at randomization date.

The OS will be compared between the two treatment arms using a two-sided stratified log-rank test at an overall two-sided 0.05 significance level. The HR for OS will be estimated using a stratified Cox model, and two-sided 95% CIs for the HR will be provided.

The OS will be compared between the two treatment arms at [REDACTED] interim analyses and [REDACTED] final analysis. [REDACTED]
[REDACTED]
[REDACTED]

To control the overall type I error rate at the 0.05 level (two sided), the secondary endpoint OS will be evaluated for statistical significance at the 5% level (two sided) only if the primary PFS endpoint meets statistical significance. The Lan–DeMets implementation ([Lan and DeMets 1983](#)) of the O’Brien–Fleming use function will be used to control the type I error at the 5% level (two-sided) for the OS evaluation in the interim and final analyses. See Section [4.10.2](#) for details.

Stratified analyses will incorporate the same stratification factors for the analysis of PFS.

Kaplan–Meier methodology will be used to [REDACTED]
[REDACTED]. The 95% CI of the [REDACTED] will be constructed using the Brookmeyer and Crowley method ([Brookmeyer and Crowley 1982](#)).

As a sensitivity analysis, an unstratified log–rank test will be performed and the unstratified HR will be provided.

4.4.2.5 Patient-Reported Outcomes

The data from the ITT population will be used to assess time to deterioration (TTD) in global health status (items 29 and 30 of the EORTC QLQ-C30) and TTD in physical functioning (items 1–5 of the EORTC QLQ-C30) for each treatment arm. TTD in global health status is defined as the time from randomization to first observed ≥ 10 point decrease in EORTC QLQ-C30 linearly transformed global health status scale score that is sustained for two consecutive assessments or followed by death while the patient is on treatment. TTD in physical functioning is defined as the time from randomization to first observed ≥ 10 -point decrease in EORTC QLQ-C30 linearly transformed physical functioning scale score that is sustained for two consecutive assessments or followed by death while the patient is on treatment. Data for patients who do not achieve a 10-point decrease will be censored at the last time patient-reported outcome (PRO) data are available. Randomized patients without baseline PRO assessment or post-baseline PRO assessment will be censored at randomization.

TTD in global health status and physical functioning will be compared between the treatment groups using the same method as the analysis of PFS.

4.4.3 Exploratory Efficacy Endpoints

4.4.3.1 PFS, DOR, and ORR

4.4.3.2 Patient-Reported Outcomes

4.4.3.2.1 Analyses of Study Conduct

On the ITT population, completion analysis will be performed for the overall EORTC QLQ-C30 questionnaire. Completion rates will be summarized by number and proportion of patients among those expected to complete the EORTC QLQ-C30 at each time point. Reasons for non-completion may be summarized.

4.4.3.2.2 Visit Score Summary and Change from Baseline

PRO-evaluable population will include all randomized patients who have a baseline and at least 1 post-baseline assessment. On the PRO-evaluable population, visit summary and change from baseline analyses will be performed for the EORTC QLQ-C30 scales. Summary statistics (number of patients, mean, standard deviation, median, minimum, maximum) of score(s) and score change(s) will be presented by treatment arm from baseline to each time point including time of disease progression per RECIST v1.1, at treatment discontinuation, and post-study treatment.

4.4.3.2.3 Responder Analysis

On the PRO-evaluable population, the number and proportion of patients with a clinically 10-point meaningful change will be summarized by treatment arm, for the EORTC QLQ-C30 scores at the same timepoints listed in Section 4.4.3.2.2. The 95% CI around the proportion will be calculated using the Clopper–Pearson method for each treatment arm.

The difference in the proportions between the two treatment arms will be presented with a two-sided 95% CI based on a normal approximation to the binomial distribution.

4.4.3.2.4 Mixed-Effect Model Repeated Measures Analysis

On the PRO-evaluable population, mixed-effects model repeated measures (MMRM) will be used for comparing the EORTC QLQ-C30 Role Functioning (RF), Physical Functioning (PF), and Global Health Status/Health-Related Quality of Life (GHS/HRQoL) scores between treatment arms. The model may include a term for intercept, a term for linear time trend, a term for treatment group, and a term for treatment-by-time interaction. Repeated measures over time may be accounted for by covariance structure. Time points with less than 20% patients who completed the RF, the PF, or the GHS/HRQoL scales, where all subsequent time points also have less than 20% completion will be excluded.

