3. STUDY DESIGN

3.1 DESCRIPTION OF THE STUDY

Study CO39262 is a Phase III, double-blinded, placebo-controlled, randomized, multicenter study designed to evaluate the efficacy, safety, and pharmacokinetics of atezo+cobi+vem compared with placebo+cobi+vem in patients with previously untreated *BRAF^{V600}* mutation-positive metastatic or unresectable locally advanced melanoma. The primary endpoint of the study is PFS.

[figure not shown]
Approximately 500 patients will be randomized in the study. Patients will be randomized in a 1:1 ratio to Arm A (placebo+cobi+vem) or Arm B (atezo+cobi+vem). Patients in both arms will be treated with cobimetinib and vemurafenib during a run-in period of 28 days. Patients in Arm A (control arm) will receive atezolizumab placebo, cobimetinib, and vemurafenib (960 mg twice daily [BID]). Patients in Arm B (experimental arm) will receive active atezolizumab, cobimetinib, and vemurafenib (720 mg BID) (see Section 3.3.2 for rationale for dosing regimen).

As the vemurafenib doses are different between the two treatments arms, vemurafenib will be blinded in both study arms. To ensure adequate blinding, patients in both arms will receive the same number of vemurafenib tablets, with patients in Arm A receiving all active vemurafenib tablets and patients in Arm B receiving a combination of active vemurafenib tablets and vemurafenib placebo tablets, as described in [Table 2](#).

Following randomization, patients will enter a 28-day run-in period to receive treatment with cobi+vem, followed by treatment with either atezo placebo+cobi+vem (Arm A) or atezo+cobi+vem+vem placebo (Arm B) in the triple combination period, as outlined in [Table 2](#).

A study schema is presented in [Figure 2](#). The treatment regimens for Arms A and B are described in [Table 2](#).

Figure 2 Study Treatment Schema

21/7=treatment on Days 1–21 followed by no treatment on Days 22–28; BID=twice daily;

PS=performance status; QD=once daily; Q2W=every 2 weeks; R=randomization;

RECIST v1.1=Response Evaluation Criteria in Solid Tumors, Version 1.1.

- ^a Study treatment will continue until investigator-determined disease progression according to RECIST v1.1 (or subsequent clinical deterioration or confirmed disease progression 4–8 weeks later, for clinically stable patients with a favorable benefit-risk ratio), death, unacceptable toxicity, withdrawal of consent, or pregnancy, whichever occurs first.

Table 2 Treatment Regimens for Arm A and Arm B

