2.3 DETERMINATION OF SAMPLE SIZE

Approximately 500 patients will be randomized into the study.

The final analysis of the primary endpoint of PFS will take place when approximately [REDACTED] PFS events have occurred. Statistical considerations are based on the following assumptions:

- Stratified log-rank test at 0.05 significance level (two sided)
- [REDACTED]
- [REDACTED]
- [REDACTED]
- [REDACTED]
- [REDACTED]
- [REDACTED]

A total of [REDACTED] PFS events provides approximately [REDACTED] % power to detect an improvement in median PFS from [REDACTED]

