4.4 EFFICACY ANALYSES

Unless otherwise noted, all efficacy analyses will include the ITT population, and patients will be grouped according to the treatment assigned at randomization. The stratification factors will be those used for randomization and will be obtained from the IWRS (geographic region and baseline LDH). Due to the potential risk of over-stratification ([Akazawa et al., 1997](#)), if at least one stratum (i.e., a combination of stratification factor levels across geographic region and baseline LDH) has fewer than 10 PFS events across treatment arms, the stratification factor (one of two stratification factors: geographic region and baseline LDH per IWRS) which contains the level with the smallest number of patients will be removed from the stratified analyses. The removal of the stratification factors will continue until there is no stratum with fewer than 10 PFS events. The final set of stratification factors used in stratified analyses will be applied to all endpoints where stratified analyses are planned.

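### The exploratory QLQ-C30 mixed model names only linear time, treatment and their interaction; adding baseline score, categorical visit and strata, and fixing the covariance and contrast, would be a free improvement

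*SAP*

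**What the plan says.** SAP 4.4.3.2.4, under the exploratory efficacy endpoints, plans a mixed model comparing role functioning, physical functioning and global health status between arms. On its terms it says "The model may include a term for intercept, a term for linear time trend, a term for treatment group" "and a term for treatment-by-time interaction". On correlation it says "Repeated measures over time may be accounted for by covariance structure". It does not say whether the baseline score is one of the modelled visits, where time zero lies, or whether the comparison is a slope, a difference at a visit or an average.

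The analysis set is defined in SAP 4.4.3.2.2: "PRO-evaluable population will include all randomized patients who have a baseline and at least 1 post-baseline assessment". Baseline is therefore available for everyone analysed.

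Region and LDH are held in the IWRS. SAP 4.4 states how far they reach: "The final set of stratification factors used in stratified analyses will be applied to all endpoints where stratified analyses are planned". The mixed model is not described as stratified.

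On timing, Protocol 3.1 says "Following randomization, patients will enter a 28-day run-in period to receive treatment with cobi+vem". Protocol Table 2 gives both arms the same regimen on Run-In Days 1-21, a vemurafenib difference from Day 22, and atezolizumab or its placebo from Cycle 1 Day 1. The schedule places randomisation no more than 24 hours before Run-In Day 1.

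**The concern.** This is the plan's only model-based comparison of mean QLQ-C30 scores. Two features of the named terms stand out.

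First, a baseline score exists for every patient in the set and usually predicts later scores, yet it is not named as a covariate. Nor are the strata.

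Second, time enters as a straight line, although the arms are treated identically for three weeks and the added drug starts in week five. A difference that opens after the run-in and then stays flat, or that appears briefly and resolves, does not have that shape. The SAP allows for a delayed effect on the time-to-event endpoints with a late-weighted log-rank test (4.4.5.3), but makes no similar allowance here.

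At stake are the width of the intervals for a level difference and the week to which a difference is attributed.

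**Working it through.** The documents give no SD, correlation or effect size for this model, so there is no stated figure to reproduce. Everything below rests on labelled assumptions.

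**1. Baseline score, level contrast at one visit.** With correlation r between baseline and follow-up, SE(adjusted)/SE(unadjusted) = √(1 − r²). The equivalent sample-size factor is 1/(1 − r²).

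| r (assumed) | SE ratio | SE reduction | Equivalent extra patients |
|---|---|---|---|
| 0.4 | √0.84 = 0.917 | 8% | 1/0.84 → 19% |
| 0.5 | √0.75 = 0.866 | 13% | 1/0.75 → 33% |
| 0.6 | √0.64 = 0.800 | 20% | 1/0.64 → 56% |

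**2. Does the gain hold for other contrasts?** SAP 2.3 says "Approximately 500 patients will be randomized into the study", so at most about 250 per arm enter. I assumed SD 20, r = 0.5, complete data and repeated visits to Week 48, and applied generalised least squares to the named terms.

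| Contrast | Compound symmetry: SE without → with baseline covariate | Decaying correlation: SE without → with baseline covariate |
|---|---|---|
| Level difference at Week 24 | 1.31 → 0.96 | 1.16 → 0.98 |
| Arm-by-time slope, per week | 0.0237 → 0.0237 | 0.0391 → 0.0378 |

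If baseline is instead a modelled response and the contrast is change from Week 0, the SE is already 0.52 (compound symmetry) or 0.88 (decaying). The loss therefore applies to a level contrast that ignores baseline. It is close to nil for the slope.

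**3. Strata.** SE ratio = √(1 − R²). An assumed R² of 2%, 5% or 10% gives 0.990, 0.975 or 0.949, a reduction of about 1-5%.

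**4. Straight-line time.** Let D(t) be the true arm difference at week t. The fitted line a + bt minimises Σ w(t)·[D(t) − a − bt]². Visits are every 4 weeks to Week 48, so Week 8 is Cycle 2 Day 1 and Week 48 is Cycle 12 Day 1. Weights fall with an assumed 11-month median (47.8 weeks): w(t) = 0.5^(t/47.8). Each curve is fitted with and without Week 0 as a modelled visit.

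| True curve (assumed) | Fitted line, Week 0 in | Fitted line, Week 0 out | Fit at Week 8 | Fit at Week 48 |
|---|---|---|---|---|
| 0 to Week 4, then 5 | 2.11 + 0.0895t | 3.09 + 0.0581t | 2.8 and 3.6 (true 5) | 6.4 and 5.9 (true 5) |
| 8 at Weeks 8 and 12, else 0 | 3.00 − 0.0734t | 4.39 − 0.1180t | 2.41 and 3.45 (true 8) | −0.5 and −1.3 (true 0) |
| Ramp from 0 at Week 4 to 5 at Week 48 | −0.31 + 0.1090t | −0.45 + 0.1136t | 0.56 and 0.45 (true 0.45) | 4.9 and 5.0 (true 5) |

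With Week 0 in, the first curve shows about 2 points at Week 0, when the true difference is zero. The generalised least-squares version, with denser early visits, gives 2.0-3.0 there. For the ramp, the error is at most about 0.5 points at any week checked.

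**The case against.** A reader might infer that the SAP commits to a straight line, that precision is lost whatever is reported, and that the model's visit-level estimates will be wrong. The documents do not support that stronger reading, for five reasons.

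- **The wording is permissive.** The terms are ones the model may include. A straight line is not fixed, and baseline, strata or categorical visit are not barred. Nor does the section promise visit-level model estimates.
- **The two harms largely belong to different readings.** If baseline is a modelled response, the line crosses the run-in but baseline information is already used for a change contrast. If it is not, the precision loss can apply, but modelled time starts near the end of the run-in. Even then a step effect is still misfitted, as the Week 0 out column shows.
- **The size depends on the contrast and the true curve.** The named interaction estimates a slope, for which baseline adds almost nothing. A ramp fits well.
- **The divergence is not exactly at the end of the run-in.** Vemurafenib already differs on Days 22-28.
- **Unsmoothed results are planned.** SAP 4.4.3.2.2 gives mean scores and changes by arm at each time point. SAP 4.4.3.2.3 gives the arm difference in proportions with a 10-point change, with a confidence interval, at the same time points. An early dip would be visible there.

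All of this stands, and it limits the point. It does not remove it. The only model the SAP describes is weaker than one that could be fitted to the same data, and the permissive wording leaves terms, covariance and contrast open until the data are seen. The text of Protocol 6.4.3 is not visible, so a fuller model there can be neither confirmed nor excluded.

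**Conclusion.** The point holds as a low-priority improvement. If the named model is fitted and a level contrast is reported without using baseline, the standard error would be about 8%, 13% or 20% lower with baseline adjustment, at assumed correlations of 0.4, 0.5 or 0.6. There is little or no gain for a slope contrast, a smaller gain if baseline is already a response, and about 1-5% from strata at an assumed R² of 2-10%.

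A linear arm-by-time term can misplace a step or transient difference. A constant 5-point gap after the run-in becomes about 2.8-3.6 at Week 8 and 5.9-6.4 at Week 48. An 8-point dip at Weeks 8-12 becomes about 2.4-3.5 at Week 8. For scale, Protocol 4.5.8.1 takes 10 points as clinically meaningful. A steady ramp from Week 4 is off by only about 0.5 points.

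Correlations, R², curves, visit grid and weights are all assumptions; only the listed terms, the population and the treatment timing come from the documents. Consequence is limited: the analysis is exploratory with no alpha allocated, and the secondary patient-reported endpoints are times to deterioration analysed like PFS (SAP 4.4.2.5).

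**What to change.** Replace the permissive list in SAP 4.4.3.2.4 with a committed model:

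- **Outcome:** post-baseline score, or change from baseline, at each scheduled visit.
- **Fixed effects:** treatment, visit as a categorical factor, treatment-by-visit, baseline score (optionally baseline-by-visit), and the final set of strata (region and LDH per IWRS).
- **Covariance:** a named structure, with a stated fallback if it does not converge.
- **Contrast:** arm differences by visit, and averaged over post-run-in visits, each with a 95% confidence interval.

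The cost is SAP wording only. Baseline scores and strata are already collected, and conditioning on baseline excludes nobody from the PRO-evaluable set. The change should be made before the data are unblinded.

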4.4.4 Exploratory

4.4.5 Sensitivity Analyses

4.4.5.1 Missing Tumor Assessment

The impact of missed scheduled tumor assessments on PFS will be assessed. If patients missed two or more consecutive assessments scheduled immediately prior to the date of disease progression per RECIST v1.1 or death, a sensitivity analysis will be performed where patients who missed two or more scheduled assessments immediately prior to the date of disease progression per RECIST v1.1 or death will be censored at date of the last tumor assessment prior to the missed visits, or at randomization date if no post-baseline tumor assessment prior to the missed visits.

4.4.5.2 Non-Protocol Anti-Cancer Therapy

A sensitivity analysis will also be conducted on PFS to determine the impact on non-protocol anti-cancer therapy. Patients who received non-protocol anti-cancer therapy will be censored at the date of the last tumor assessment prior to start of non-protocol anti-cancer therapy, or randomization date if no post-baseline tumor assessment prior to start of non-protocol anti-cancer therapy.

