All patients will be closely monitored for safety and tolerability throughout the study. The National Cancer Institute Common Toxicity Criteria for Adverse Events, Version 4.0 (NCI CTCAE v4.0) will be used to characterize the toxicity profile of the study treatments for all patients. The protocol includes a detailed risk management plan for monitoring and managing molecule-specific and potential combination toxicities (see Section 5.1).

Tumor response will be evaluated by the investigator and by an independent review committee (IRC) according to RECIST v1.1 (see [Appendix 4](#)). [REDACTED] will only be assessed by the investigator (Eisenhauer et al. 2009; see [Appendix 5](#)). All measurable and non-measurable lesions will be documented at screening. Response will be assessed by the investigator at 8- or 12-week intervals (see Section 4.5.5 for details) until investigator-determined disease progression (according to RECIST v1.1) or death, whichever occurs first. Patients who experience disease progression (RECIST v1.1) must have scans repeated 4–8 weeks after initial documentation of progression to confirm disease progression as required per the protocol. Tumor assessments (RECIST v1.1 [REDACTED]) are to continue according to schedule in patients who discontinue treatment for reasons other than confirmed disease progression.

Clinically stable patients who have a favorable benefit-risk ratio should continue on study treatment following radiographic progression per RECIST v1.1 at least until a follow-up scan 4–8 weeks later. Patients who continue treatment beyond radiographic disease progression will be closely monitored. Treatment will be discontinued if clinical deterioration due to disease progression occurs at any time or if persistent disease growth is confirmed by follow-up scans performed 4–8 weeks later. If the follow-up scans do not confirm disease progression, the patient may continue on study treatment.

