3.2 END OF STUDY AND LENGTH OF STUDY

The study will end when all patients enrolled have been followed until death, withdrawal of consent, lost to follow-up, or the Sponsor decides to end the trial, whichever occurs first. Patients may continue on study treatment until the development of progressive disease, unacceptable toxicity, and/or consent withdrawal. Patients who discontinue study treatment for any reason will be followed for safety according to protocol, followed for disease progression and followed for survival until death, withdrawal of consent, or they are lost to follow-up. Patients who start subsequent anti-cancer treatment after study treatment discontinuation will still need to be followed for disease progression, survival, and safety per the protocol. The length of the study, from screening of the first patient to the last patient last visit, is expected to be approximately 90 months.

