4.4.2 Prohibited Therapy

Use of the following concomitant therapies is prohibited as described below:

Prohibited therapies applicable to all patients

- Concomitant therapy intended for the treatment of cancer (including, but not limited to, chemotherapy, hormonal therapy, immunotherapy, radiotherapy for palliative or other purposes, and herbal therapy), whether health authority-approved or experimental, is prohibited for various time periods prior to starting study treatment, depending on the agent (see Section 4.1.2), and during study treatment until disease progression is documented and the patient has discontinued study treatment.
- Investigational therapy is prohibited during the study.
- Anti-emetic medications, antidiarrheal medications, and hematopoietic growth factors are not to be administered prophylactically prior to initiation of study treatment.
- Anti-arrhythmic agents and medications with a risk of torsades de pointes are prohibited within 7 days prior to initiation of study treatment, during study treatment, and for 30 days after the final dose of study treatment.
- Acetaminophen is prohibited within 7 days prior to initiation of study treatment, during study treatment, and for 30 days after the final dose of study treatment, unless the patient has an absolute contraindication to the use of non-steroidal anti-inflammatory drugs (NSAIDs) or aspirin (i.e., severe allergy or reactive airway disease sensitive to NSAIDs or aspirin).

Prohibited therapies applicable to patients receiving atezolizumab (or atezolizumab placebo)

- Denosumab (a RANKL inhibitor) is prohibited during atezolizumab treatment because it could potentially alter the efficacy and safety of atezolizumab. Patients who are receiving denosumab prior to enrollment must be willing and eligible to receive a bisphosphonate instead while in the study.
- Live, attenuated vaccines (e.g., FluMist®) are prohibited within 4 weeks prior to initiation of atezolizumab, during atezolizumab treatment, and for 5 months after the final dose of atezolizumab.
- Systemic immunostimulatory agents (including, but not limited to, interferons and IL-2) are prohibited within 4 weeks or five half-lives of the drug, whichever is longer, prior to initiation of atezolizumab and during atezolizumab treatment because these agents could potentially increase the risk for autoimmune conditions when given in combination with atezolizumab.

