4.6.2 Study Treatment Discontinuation

Patients must permanently discontinue study treatment if they experience any of the following:

- Disease progression per investigator assessment according to RECIST v1.1 (confirmed as per [Section 3.1](#))
- Clinical deterioration due to disease progression
- Use of an anti-cancer therapy (outside of study treatment per protocol)
- Pregnancy
- Withdrawal of consent
- Any medical condition that the investigator or Sponsor determines may jeopardize the patient's safety if he or she continues to receive study treatment
- Investigator or Sponsor determines it is in the best interest of the patient (e.g., unwillingness to comply with study assessments that compromise their safety)
- Any adverse event that requires study treatment discontinuation per the guidelines in [Section 5.1](#)
- Intolerance of study treatment despite undergoing protocol-defined dose reduction
- In cases where discontinuation of one or two study drugs is required for toxicity, patients may continue on the remaining drug(s) per the guidelines in [Section 5.1](#)

Patients who discontinue atezolizumab will return to the clinic for an atezolizumab treatment discontinuation visit 28 (± 7) days after the final dose of atezolizumab. The visit at which response assessment shows disease progression may be used as the treatment discontinuation visit, provided all required assessments have been performed and it is 28 (± 7) days after the final dose of study drug. The primary reason for study treatment discontinuation should be documented on the appropriate eCRF. Patients who discontinue study treatment will not be replaced.

If study treatment is discontinued prior to progressive disease, tumor assessments should continue according to the protocol schedule until investigator-assessed disease progression according to RECIST v1.1.

After treatment discontinuation, information on survival follow-up and subsequent anti-cancer therapy will be collected via telephone calls, patient medical records, and/or clinic visits approximately every 12 weeks until death (unless the Sponsor terminates the study). If the patient withdraws from the study, the study staff may use a public information source (e.g., county records) to obtain information about survival status only as is permissible per local laws and regulations.

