4.4.1 Primary Efficacy Endpoint

The primary efficacy analysis will be the comparison of PFS, as determined by the investigator, between the two treatment arms using the stratified log-rank test at an overall 0.05 significance level (two-sided).

The statistical hypothesis of this study is as follows:

- H_0 : PFS (Arm A)=PFS (Arm B)
- H_1 : PFS (Arm A)≠PFS (Arm B)

PFS (Arm A) represents the survival function of PFS in the placebo+cobi+vem arm, and PFS (Arm B) represents the survival function of PFS in the atezo+cobi+vem arm.

PFS, as assessed by the investigator, is defined as the time from randomization to the first occurrence of disease progression, as determined by the investigator according to RECIST v1.1, or death from any cause, whichever occurs first. Data for patients who have not experienced disease progression or death at the time of analysis data cut-off will be censored at the date of last tumor assessment. Data for patients without post-baseline tumor assessment will be censored at randomization date.

The hazard ratio (HR) for PFS will be estimated using a stratified Cox model, and two-sided 95% CIs for the HR will be provided. Results from an unstratified analysis will

also be presented. Kaplan-Meier methodology will be used to estimate the median PFS for each treatment arm, and Kaplan-Meier curves will be produced. The 95% CI of the median PFS for each treatment arm will be constructed using the Brookmeyer and Crowley method ([Brookmeyer and Crowley 1982](#)).

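### SAP 4.4.5.2 does not limit censoring to non-protocol therapy started before progression or death, so this sensitivity analysis of PFS can be programmed in two ways with different hazard ratios

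*SAP*

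**What the plan says.** SAP 4.4.5.2 sets the rule: "Patients who received non-protocol anti-cancer therapy will be censored at the date of the last tumor assessment prior to start of non-protocol anti-cancer therapy", or at randomization if there is no earlier post-baseline scan. The class is every recipient, and the sentence puts no condition on when the therapy began relative to the PFS event.

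Four other places bear on how to read it:

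- SAP 4.4.1, the primary rule, restricts censoring to patients without an event: "Data for patients who have not experienced disease progression or death at the time of analysis data cut-off will be censored".
- SAP 4.4.5.1, the missed-scan rule, is anchored to the event date: patients who "missed two or more scheduled assessments immediately prior to the date of disease progression per RECIST v1.1 or death will be censored".
- The closing paragraph of SAP 4.4.5.3 says that the sensitivity analyses use methods analogous to those for PFS or OS. It gives no order of precedence between an event and a censoring date.
- Protocol 4.4.2 prohibits other cancer therapy "during study treatment until disease progression is documented and the patient has discontinued study treatment".

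The Protocol describes no such sensitivity analysis, and SAP sections 1 and 4 say that the SAP takes precedence for filing. The wording of 4.4.5.2 therefore has to stand by itself.

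**The concern.** The analysis is meant to show whether non-protocol therapy affected the PFS result. Only therapy started before progression or death can do that. Under Protocol 4.4.2, though, most recipients should start it after progression, when the endpoint has already been reached.

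For those patients the last scan before the new therapy is either the progression scan or a later one. Protocol 3.1 says that patients who progress "must have scans repeated 4–8 weeks after initial documentation of progression to confirm disease progression". Take a patient who progresses at Week 32, has the confirmation scan at Week 38 and starts new therapy at Week 39. The literal rule censors this patient at Week 38, six weeks after the recorded progression. Without a confirmation scan, the censoring falls on the day of progression itself.

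The result would then depend on what patients received after the endpoint. If that differed by arm, the analysis could contradict or exaggerate a sound primary result for reasons unrelated to PFS.

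**Working it through.** **No plan figure to reproduce.** The SAP gives no figure for this analysis, and the planned event count, medians and target hazard ratio are redacted in the public documents. The size below is therefore a range over assumptions.

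**Inputs from the documents**

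- About 500 patients, 1:1 (SAP 2).
- Scans every 8 weeks through 24 months (Protocol 4.5.5).
- Confirmation scan 4–8 weeks after progression (Protocol 3.1); 6 weeks used.
- Control median PFS of 12 months, within the 11–14 months quoted in Protocol 1.1; 11 and 14 also run.

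**Assumptions not in the documents**

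- Exponential PFS with a true hazard ratio of 0.70.
- 10% of events are deaths without progression.
- 5% of patients start other therapy before progression.
- Mean delay from progression to new therapy of about 1.75 months.
- 15 months of accrual and at least 14 months of follow-up.
- Uptake after progression varied by arm.

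**Closed form.** Let d be the share of events that are deaths, and pA and pB the uptake after progression. The literal rule keeps a fraction d + (1 − d)(1 − p) of an arm's events, so

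HR(literal) = HR(true) × [d + (1 − d)(1 − pB)] / [d + (1 − d)(1 − pA)].

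With d = 0.10, the kept fractions are:

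- 40% uptake: 0.1 + 0.9 × 0.6 = 0.64
- 50% uptake: 0.1 + 0.9 × 0.5 = 0.55
- 60% uptake: 0.1 + 0.9 × 0.4 = 0.46
- 70% uptake: 0.1 + 0.9 × 0.3 = 0.37

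**Simulation.** 400 trials per scenario, unstratified log-rank and Cox, error about 2 percentage points on power. The primary analysis has about 311 events, a hazard ratio of about 0.71 and 87–91% power.

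| Uptake A/B | Closed form | Simulated HR | Events | Significant for Arm B |
|---|---|---|---|---|
| 40%/40% | 0.70 | 0.71 | 194 | 69% |
| 60%/60% | 0.70 | 0.70 | 144 | 59% |
| 50%/40% | 0.70 × 0.64/0.55 = 0.81 | 0.81 | 182 | 29% |
| 60%/40% | 0.70 × 0.64/0.46 = 0.97 | 0.95 | 167 | 5% |
| 70%/50% | 0.70 × 0.55/0.37 = 1.04 | see below | – | – |
| 40%/60% | 0.70 × 0.46/0.64 = 0.50 | 0.52 | 173 | 99% |

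The 70%/50% case was simulated under a different set-up (control median 11 months, 18 months of accrual, cut-off at 36 months). It also gave about 1.04, with about 170 events.

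Event loss at equal uptake is 1 − 194/311 = 38% at 40%, and 1 − 144/311 = 54% at 60%. A control median of 11 or 14 months gives 0.95–0.96 at 60%/40%.

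**Rule limited to therapy before progression or death.** The hazard ratio is 0.70–0.71 in every scenario, about 295 of 311 events are kept, and power is 86–90%.

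**The case against.** The strongest reply is that the SAP already points to the sensible reading. PFS is time to the first progression or death, SAP 4.4.1 censors only patients without an event, and 4.4.5.3 carries analogous methods into the sensitivity analyses. A programmer who takes the earlier of event and censoring would keep the progression. The missed-scan rule does not contradict this, because its censoring date always falls before the event it replaces. The literal reading also defeats the purpose of the analysis. Therapy before progression is foreseen: Protocol 4.6.2 makes it a reason to stop study treatment, and Protocol 3.2 adds that "Patients who start subsequent anti-cancer treatment after study treatment discontinuation will still need to be followed for disease progression, survival, and safety per the protocol".

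Most of this stands, and it is why the defect is an ambiguity rather than a settled error. It does not remove the problem. No sentence gives the order of precedence. When the progression scan is the last scan before therapy, the two dates coincide, and an earlier-of rule does not settle the tie. SAP 4.4.5.1, one subsection before, uses the same verb to replace an observed event with a censoring.

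A reader might also infer that control patients will use more later therapy because they cannot cross over, so that the rule works against Arm B. The documents do not support this. The crossover bar blocks only a switch to the experimental arm, not other later therapy. Under Protocol 4.2, investigator, patient and Sponsor are blinded apart from limited exceptions. The direction of any imbalance is unknown.

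**Conclusion.** The point holds as a gap in the wording of one sensitivity analysis. As written, two competent programmers could report different hazard ratios from the same data, and the literal version would be wrong for its purpose.

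The size rests on assumed uptake. With equal uptake the hazard ratio does not move, and the harm is lost events and power. With a 10- to 20-point imbalance at a true ratio of 0.70, the literal result runs from about 0.52 (more use in Arm B) to about 0.81–1.04 (more use in Arm A).

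Three stronger readings go too far:

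- That the rule will remove or reverse the PFS effect. This needs markedly higher uptake in Arm A, and the documents give no uptake by arm.
- That it discards more than half the events. This holds near 60% uptake; at 40% the loss is about 38%.
- That the trial's main conclusion is at risk. The primary PFS test, its type I error and the condition that opens OS testing do not use this rule.

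**What to change.** Replace the censoring sentence in SAP 4.4.5.2 with:

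*Patients who start non-protocol anti-cancer therapy before documented progression per RECIST v1.1 or death will be censored at the last tumor assessment before the start of that therapy (or at randomization if there is none). Progression or death on or before the start date of that therapy is counted as an event.*

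The second sentence settles therapy that starts on the day of progression. The change costs one or two sentences in the SAP. It needs no new data and leaves the primary analysis as it is.
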